**Table 9.5.2–1: Sample size obtained for various precisions and proportions**

Margin of error for 95% CI				
Proportion	5%	4%	3%	2%
10%	139	216	384	864

30%	323	504	896	2,017
50%	384	600	1,067	2,401
70%	323	504	896	2,017
90%	139	216	384	864

Since the proportion of physicians informed about the updated prescribing conditions and recommendations for safe use of systemic thiocolchicoside is not known and there is no evidence supporting the expected proportion, the worst case hypothesis will be assumed considering that 50% of physicians will have received and understood the safety information distributed recently. This assumption yields the largest sample size.

Considering this hypothesis and in order to achieve a CI of 95% with a half-width of 4%, a total of 600 analysable physician questionnaires will be needed for the overall sample. Considering a margin of error of 5% (or 3% respectively) instead of 4%, the required sample size would be 384 (or 1,067) analysable physician questionnaires for the overall sample.

Based on IMS Medical Radar experience from previous similar surveys and estimates and the evaluation of the survey feasibility with four countries, the sample size of 600 is considered for this study. Indeed, the elected sample size should be sufficient to be divided between 4 countries and further between 3 groups of specialities.

It is estimated that about 30% of physicians will not complete the questionnaire until the end or not be analysable (i.e. physicians who respond to questions regarding their knowledge on the updated safety concerns of systemic thiocolchicoside or physicians without any prescription of systemic thiocolchicoside in the last 12 months or physicians who have to interrupt the interview due to an emergency (rare)). Taking into account these respondent physicians without analysable questionnaires, the overall sample size of 780 participating physicians will be required to reach 600 analysable questionnaires (i.e. recruitment of physicians should continue until 600 analysable questionnaires have been reached).

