**Table 9.5.2–3: Number of physician interviews required per country**

Country	Sample size objectives			
	Analysable questionnaires			ns
France	180	(30.0%)	234	(30.0%)
Greece	120	(20.0%)	156	(20.0%)
Italy	180	(30.0%)	234	(30.0%)
Portugal	120	(20.0%)	156	(20.0%)
All	600	(100.0%)	780	(100.0%)

\* Note: The country-distributions of the 'Number of participating physicians required' and the 'Number of participating physicians with complete analysable questionnaire expected' are the same, since the second one is deducted from the first one through the application of a 30% inflation rate due to physicians who will not complete the questionnaire.

At each country level, the sample size will be further divided into the selected groups of specialties.

Usually, to ensure the robustness of statistical estimations at a wished level of analysis (e.g. specialty or aggregated specialties per country), the sample size should not be lower than a threshold of 40 statistical units in each entity of this level.

For analysis, less common specialties as orthopedists or orthopedic surgeons need to be grouped. Moreover, for other less common specialties as rheumatologists, given their very limited contribution within the total of prescriptions of systemic thiocolchicoside (less than 2.5% (Table 7.2–1), the recruitment of a threshold of 40 rheumatologists and 40 orthopedists/ orthopedic surgeons who have prescribed systemic thiocolchicoside per country will be too difficult.

It will be necessary to weight the results according to the real proportion of physicians in order to determine the representativeness of the overall sample. If the threshold of 40 statistical units (physicians per specialty in a country) would not be reached, then additional

physicians of other groups will be recruited to compensate and preserve the sample size at country level.

To comply with this constraint, an arbitrary split per specialty in each selected country will be implemented as follows (Table 9.5.2–4). Whenever possible, the real breakdown of targeted specialists was used to determine the split per specialty. But most of the time, building a sample proportionally distributed by the number of specialists would yield very small numbers for less frequent specialties, mainly in Greece and Portugal.

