As a consequence, an over-sampling of less frequent specialties will be applied in order to provide a sufficient number of analysable questionnaires (threshold of 30). This allocation is applied to the number of analysable questionnaires. Then, the number of required participating physicians is deducted taking into account 30% of respondents without analysable questionnaires.

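### Section 9.5.2 adds 30% to 600 to get 780 participants, but the 30% is defined as a loss from participants: 780 then yields 546 analysable questionnaires, and 600 needs 858

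*Protocol*

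**What the plan says.** Section 9.5.2 sets the analysable sample first: "a total of 600 analysable physician questionnaires will be needed for the overall sample", from an expected proportion of 50%, a 95% confidence interval and a half-width of 4%.

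It then allows for losses: "It is estimated that about 30% of physicians will not complete the questionnaire until the end or not be analysable". From this it concludes that "the overall sample size of 780 participating physicians will be required to reach 600 analysable questionnaires". The same sentence adds in brackets that recruitment goes on until 600 analysable questionnaires are obtained. The next paragraph repeats the 780.

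The 30% is described twice more in section 9.5.2:

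- The note to Table 9.5.2–3 compares the participating and the analysable numbers and says their country distributions agree, "since the second one is deducted from the first one through the application of a 30% inflation rate".
- The paragraph before Table 9.5.2–4 says that "the number of required participating physicians is deducted taking into account 30% of respondents without analysable questionnaires".

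The participant rows of the two tables give 234 for France and Italy (117 GPs, 52 rheumatologists, 65 orthopedists) and 156 for Greece and Portugal (78, 39, 39).

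Two operating rules do not name their unit. After Table 9.5.2–4, physicians in a stratum are contacted in order of draw until the needed number of physicians is met. Section 9.6.1 stops recruitment in a stratum once its target is reached. Neither says whether participants or analysable questionnaires are counted.

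**The concern.** One percentage is used on two different bases. The loss estimate and the paragraph before Table 9.5.2–4 make it a share of physicians or respondents, that is, of the participants. The calculation uses it as a mark-up on the analysable number. The two give different answers, and the printed one is the smaller.

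A sample-size section should give a recruitment figure that follows from its own loss assumption, and this one does not. The participant rows are also the only numbers in the protocol that look like field quotas for participants. If a stratum were closed on them, it would be expected to return 91% of its analysable target. The smallest strata, planned at exactly the stated minimum of 30 analysable questionnaires, would fall below it.

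**Working it through.** **Inputs**, all from section 9.5.2: P = 0.50; half-width e = 0.04; 95% confidence (z = 1.96); loss d = 0.30; analysable targets per stratum of 90/40/50 (France, Italy) and 60/30/30 (Greece, Portugal).

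**Step 1. The analysable number.** n = P(1 − P)z²/e² = 0.25 × 1.96² / 0.04² ≈ 600.2. The stated 600 is reproduced.

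**Step 2. The participant number as printed.** 600 × (1 + 0.30) = 780. This reproduces the figure exactly. All participant quotas reproduce the same way: 90 → 117, 40 → 52, 50 → 65, 60 → 78, 30 → 39.

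**Step 3. The participant number that follows from the stated loss.** If 30% of participants are lost, the fraction 1 − d = 0.70 remains:

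- 780 × 0.70 = 546 analysable, which is 600 − 546 = 54 short.
- 600 / 0.70 = 857.1, so 858 participants; 858 − 780 = 78, or 10% more than 780.
- Loss at which 780 would give 600: 1 − 600/780 = 23.1%.

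**Step 4. By stratum**, with n/0.70 rounded to the nearest integer, as the footnote to Table 9.5.2–4 does:

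| Stratum | Analysable target | Participants printed | Expected analysable (× 0.70) | n/0.70 | Rounded |
|---|---|---|---|---|---|
| France, Italy: GPs | 90 | 117 | 81.9 | 128.6 | 129 |
| France, Italy: rheumatologists | 40 | 52 | 36.4 | 57.1 | 57 |
| France, Italy: orthopedists | 50 | 65 | 45.5 | 71.4 | 71 |
| Greece, Portugal: GPs | 60 | 78 | 54.6 | 85.7 | 86 |
| Greece, Portugal: rheumatologists | 30 | 39 | 27.3 | 42.9 | 43 |
| Greece, Portugal: orthopedists | 30 | 39 | 27.3 | 42.9 | 43 |

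Country sums: 129 + 57 + 71 = 257 and 86 + 43 + 43 = 172. Total: 2 × 257 + 2 × 172 = 858.

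**Step 5. Precision if the survey closed at 546.** Half-width at P = 0.5 by the protocol's own formula: 1.96 × √(0.25/546) = 4.19%, against 1.96 × √(0.25/600) = 4.00%.

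**Step 6. Sensitivity to the loss**, since the protocol says only about 30%:

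| Loss among participants | Participants needed for 600 | Analysable from 780 |
|---|---|---|
| 20% | 750 | 624 |
| 25% | 800 | 585 |
| 30% | 858 | 546 |
| 35% | 924 | 507 |

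**The case against.** The strongest reply is that the method is disclosed. The note to Table 9.5.2–3 speaks of an inflation rate, and under that rule every participant figure reproduces. On this view the 30% is a mark-up on analysable questionnaires, equivalent to a 23.1% loss, and nothing was miscalculated. This explains where 780 comes from but does not reconcile the text. The paragraph before Table 9.5.2–4 ties the 30% to respondents, and the note itself derives the analysable number from the participating number, which is the direction of a loss.

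The second reply concerns consequences, and most of it stands. The sentence containing 780 keeps recruitment open until 600 analysable questionnaires are reached. The country objectives are expressed in analysable questionnaires, and the allocation is applied to them. So 780 reads as a forecast, not a cap.

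A reader might infer that the survey will end 54 questionnaires short. The documents do not support that: it would require reading the contact rule after Table 9.5.2–4, or the stratum target in section 9.6.1, as the participant quota, against the explicit overall rule. The loose wording leaves that reading open, but does not make it the plan.

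A reader might also infer that the compensation budget and the timeline rest on 780. The protocol makes no such link. Section 9.6.1 gives six to seven weeks without reference to 780, section 10.2.1 describes compensation per physician without a total, and section 9.5.2 puts the number of contacts at about ten times the final analysable number.

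Last, even the worst case is small overall: 4.19% against 4.00%. The protocol already says that subgroups will not have the precision of the whole sample.

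**Conclusion.** The stated participant number is wrong on the protocol's own definition of the loss. With 30% of participants not analysable, 780 gives 546, and 600 requires 858. The error is confined to the participant figures: the 780, stated twice in the text of section 9.5.2, and the participant rows of Tables 9.5.2–3 and 9.5.2–4. The analysable targets (600 overall; 180 and 120 per country; 90/40/50 and 60/30/30 per stratum) are not derived from 780 and stand. It would be too much to say that the allocation as a whole is wrong.

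If recruitment follows the rule of 600 analysable questionnaires, final precision is unaffected and the defect is a forecast 78 participants too low. Only if strata are closed on participant quotas does the expected shortfall of 54 arise, with the 39-participant strata at about 27, below the threshold of 30.

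The figures assume that the 30% applies equally in every stratum, as the tables do. The size of the gap moves with the loss rate: 780 is enough up to a loss of about 23% and falls increasingly short above that.

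**What to change.** Settle the base of the 30%, in one of two ways.

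1. If it is a share of participants, replace 780 by 858 in both places in the text of section 9.5.2, describe the step as division by 0.70 in the note to Table 9.5.2–3, and recompute the participant rows as n/0.70 with nearest-integer rounding. France and Italy become 129/57/71 = 257 each, Greece and Portugal 86/43/43 = 172 each, total 858. Take the country totals as the sums of the strata so that the table adds up.
2. If it was meant as a mark-up on analysable questionnaires, keep 780, say so, and restate the expected loss as about 23% of participants in the loss estimate and in the paragraph before Table 9.5.2–4. The protocol gives no separate basis for 23%, so this is suitable only if the mark-up was really the intention.

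In both cases, state in section 9.6.1 that a stratum closes on analysable questionnaires, and use the same unit in the contact rule after Table 9.5.2–4.

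The cost is two tables and a few sentences. The target of 600 does not change. Under the first option, the field team should plan for 78 more participants.

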**Table 9.5.2–2: Distribution of the specialties involved in the survey per country (Source: Eurostat†)**

		Family practice (GPs)	Rheumatologists	Orthopedists / orthopedic surgeons	All	All %C
France ‡	#	90,630	2,353	2,936	95,919	58.8%
	%L	94.5%	2.5%	3.1%	100%	
Greece †	#	3,494	NA	2,314	5,808	3.6%
	%L	60.2%	NA	39.8%	100%	
Italy †	#	45,203	NA	9,234	54,437	33.4%
	%L	83.0%	NA	17.0%	100%	
Portugal †	#	5,943	NA	1 071	7,014	4.3%

		Family practice (GPs)	Rheumatologists	Orthopedists / orthopedic surgeons	All	All %C
	%L	84.7%	NA	15.3%	100%	
All	#	145,270	NA	15,555	163,178	100%

†Source: Eurostat [http://ec.europa.eu/eurostat/web/products-datasets/-/hlth\\_rs\\_spec](http://ec.europa.eu/eurostat/web/products-datasets/-/hlth_rs_spec). Data for the year of 2013 (most recent year with data for all selected countries).

‡Source : CNOM (Conseil National de l'Ordre des Médecins) for France in 'Atlas de la démographie médicale en France situation au 1er janvier 2014' [http://www.conseil-national.medecin.fr/sites/default/files/atlas\\_2014.pdf](http://www.conseil-national.medecin.fr/sites/default/files/atlas_2014.pdf)

# number of physicians. %L: percentages per line, %C percentages per column. NA: Not available.

A pragmatic split will be therefore implemented (Table 9.5.2–3) to allocate a sufficient sub-sample size to the less represented countries (Greece and Portugal). To allow this over-sampling of Greece (objective of 120 analysable questionnaires instead of 21 with a proportional allocation) and Portugal (objective of 120 instead of 26, respectively), an under-sampling of the most represented countries France (objective of 180 instead of 353) and Italy (objective of 180 instead of 200) is needed in compensation.

With this sample, it will be necessary to weight the results according to the real proportion of physicians from IMS reference lists or available public information obtained through external sources (e.g. Eurostat or CNOM for France) to allow the representativeness of the overall sample.

**Table 9.5.2–3: Number of physician interviews required per country**

Country	Sample size objectives			
	Analysable questionnaires			ns
France	180	(30.0%)	234	(30.0%)
Greece	120	(20.0%)	156	(20.0%)
Italy	180	(30.0%)	234	(30.0%)
Portugal	120	(20.0%)	156	(20.0%)
All	600	(100.0%)	780	(100.0%)

\* Note: The country-distributions of the 'Number of participating physicians required' and the 'Number of participating physicians with complete analysable questionnaire expected' are the same, since the second one is deducted from the first one through the application of a 30% inflation rate due to physicians who will not complete the questionnaire.

At each country level, the sample size will be further divided into the selected groups of specialties.

Usually, to ensure the robustness of statistical estimations at a wished level of analysis (e.g. specialty or aggregated specialties per country), the sample size should not be lower than a threshold of 40 statistical units in each entity of this level.

For analysis, less common specialties as orthopedists or orthopedic surgeons need to be grouped. Moreover, for other less common specialties as rheumatologists, given their very limited contribution within the total of prescriptions of systemic thiocolchicoside (less than 2.5% (Table 7.2–1), the recruitment of a threshold of 40 rheumatologists and 40 orthopedists/ orthopedic surgeons who have prescribed systemic thiocolchicoside per country will be too difficult.

It will be necessary to weight the results according to the real proportion of physicians in order to determine the representativeness of the overall sample. If the threshold of 40 statistical units (physicians per specialty in a country) would not be reached, then additional

physicians of other groups will be recruited to compensate and preserve the sample size at country level.

To comply with this constraint, an arbitrary split per specialty in each selected country will be implemented as follows (Table 9.5.2–4). Whenever possible, the real breakdown of targeted specialists was used to determine the split per specialty. But most of the time, building a sample proportionally distributed by the number of specialists would yield very small numbers for less frequent specialties, mainly in Greece and Portugal.

As a consequence, an over-sampling of less frequent specialties will be applied in order to provide a sufficient number of analysable questionnaires (threshold of 30). This allocation is applied to the number of analysable questionnaires. Then, the number of required participating physicians is deducted taking into account 30% of respondents without analysable questionnaires.

**Table 9.5.2–4: Sample size per country and per specialty**

n (vertical % per country)*	France	Greece	Italy	Portugal	All
Number of physicians with an analysable questionnaire	180	120	180	120	600
GPs	90 (50.0%)	60 (50%)	90 (50.0%)	60 (50%)	300 (50%)
Rheumatologists	40 (22.2%)	30 (25%)	40 (22.2%)	30 (25%)	140 (23.3%)
Orthopedists / orthopaedic surgeons	50 (27.8%)	30 (25%)	50 (27.8%)	30 (25%)	160 (26.7%)
Number of participating physicians required	234	156	234	156	780
GPs	117 (50%)	78 (50%)	117 (50%)	78 (50%)	390 (50%)
Rheumatologists	52 (22.2%)	39 (25%)	52 (22.2%)	39 (25%)	182 (23.3%)
Orthopedists / orthopaedic surgeons	65 (27.8%)	39 (25%)	65 (27.8%)	39 (25%)	208 (26.7%)

\* To be aligned with the n by country, numbers n per specialty have been rounded to the most closed integer.

Since the relative weight of each country and of each specialty in the sampling plan is different from its real relative weight in estimations, the extrapolation of the raw survey results to the overall target population would not be relevant.

A sample adjustment will be performed. The survey results will be weighted to reflect the real proportion of the four countries and within each country to reflect the real proportion of each specialty in order to extend the survey results to the overall target population. Both unweighted (i.e. raw data) and weighted results will be presented in the report.

A weight variable will be applied to each statistical unit (i.e. the analysable physician) during the results calculation in order to correct any over-or under-sampling that may have occurred for a country or specialty. This weight variable will indicate how many unit(s) of the population of interest an observation will count in a statistical procedure. Its value will change per country and per specialty. The weights will be normalised to obtain their sum equal to the sample size.

In order to fill-in each stratum of the sample survey from the IMS OneKey reference files, an independent sample will be selected per stratum through a simple random sampling without replacement.

In each specific stratum, physicians will be contacted according to the order of draw in this stratum. If a physician does not want to participate in the survey, the next one in order of

draw will be contacted, and so on until the required number of physicians is met. If the target for a stratum is not achieved after the end of the initial list, an additional randomly sampled list will be prepared and the physicians contacted until the goal is reached or no names are left in that stratum. If the complete list of the IMS OneKey reference files has been exhausted in any particular stratum, a strategy will be determined to adjust the sample size within stratum with associated weighting.

In web surveys, the number of physicians to be contacted for reaching the required number of physicians with analysable questionnaires is usually around ten times more than the expected final number.

It is to be noted that this sample is calculated to be representative as a whole (including all countries), not per country or specialty. Thus the subgroup analyses will not guarantee the same confidence intervals as the whole sample. Indeed per country, a sub-sample of 180 analysable questionnaires for France and Italy will allow the estimation of the unknown expected proportion (supposed to be 50% for the sample size calculation) with a margin error of 7%. For Greece and Portugal, with 120 analysable questionnaires, the expected margin error will be around 9%.

### **Sample of collected prescriptions:**

For the data on prescriptions, the statistical unit considered will be the individual drug prescription to patient. Although the level of contribution to this section per interviewed physician is not known and will depend both on the market sells of systemic thicolchicoside in each country and for each specialty, and on the percentage of interviewed physicians who prescribed the drug to patients. Physicians are requested to report up to 5 last prescriptions of systemic thicolchicoside written over the last 12 months before the survey, each pertaining to a unique patient.

As a result, the sampling method (systematic sampling) is expected to allow generalisability of results once the overall sample of physicians can be shown to be generalisable.

Based on IMS Medical Radar experience from previous similar surveys, it is estimated that in average each interviewed physician who prescribed systemic thicolchicoside to patients will contribute with 3 prescriptions on average.

If a conservative rate of 50% is assumed to evaluate the part of interviewed physicians who prescribed systemic thicolchicoside to patients, the sample size for prescriptions will be about 900, thus largely sufficient for the study of proportions of appropriate use of drug under the same assumptions of confidence interval and precision as described above.

Note that a sample adjustment will be also implemented for the sample of collected prescriptions using the same methodology as for analysable questionnaires but with different weights.

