#### **4.10 Milestones**

- Start of data collection: September 2016
- End of data collection: November 2016
- Submission of study report to EMA: June 2017

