**6. MILESTONES**

Milestone	Planned date
Registration in the EU PAS register	November 2015
Start of data collection	September 2016
End of data collection	November 2016
Final report of study results	June 2017

The table below summarises per country the time schedule of distribution of DHPC and EM.

	France	Greece	Italy	Portugal
Distribution of DHPC	April 2014	February 2014	February 2014	February 2014
Distribution of EM	26 April 2016	2 August 2016	October 2015	September 2015

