### 8.2 OBJECTIVE

The survey objective is to measure the effectiveness of the DHPC and EM, implemented as part of RMMs, by ascertaining the proportion of targeted physicians who understood and implemented the latest prescribing conditions and safety information about systemic thicolchicoside provided in the DHPC and EM.

Specific objectives were to evaluate the proportion of physicians who:

- prescribe systemic thicolchicoside only as adjuvant treatment of painful muscle contractures associated with acute spinal pathology in adults and in adolescents from 16 years onwards.
- do not prescribe systemic thicolchicoside for long-term treatment of chronic conditions.
- follow the recommendations regarding the doses and duration restriction:
  - for oral forms: the recommended and maximal dose is 8 mg every 12 hours, i.e. 16 mg per day. The treatment duration is limited to 7 consecutive days.
  - for IM forms: the recommended and maximal dose is 4 mg every 12 hours, i.e. 8 mg per day. The treatment duration is limited to 5 consecutive days.
- do not prescribe systemic thicolchicoside during pregnancy and lactation.
- do not prescribe systemic thicolchicoside in women of childbearing potential not using adequate contraception.

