### 5) Awareness of and attitude towards the latest prescribing conditions and safety information:

- Awareness of the prescribing conditions and safety information about systemic thiocolchicoside presented in the DHPC and EM:

- Awareness of the prescribing conditions and safety information: main concerns perceived
- Sources of knowledge
- Reception of the DHPC by the physician and awareness about the EM
- Physician's intention to consider the prescribing conditions and safety warnings

6) Recent prescriptions details:

The following information related to up to the last five prescriptions to patients will be collected upon physician's recall memory:

- Approximate date of prescription of systemic thiocolchicoside
- Approximate patient' age at the time of prescription (age ranges: <16 or ≥16 years old)
- Gender
- Status at the visit for females of childbearing potential (using or not an effective method of contraception, pregnant or not, planning to be pregnant, breastfeeding)
- Indication for which the drug was prescribed
- Form, number of administrations and dose per administration per day
- Duration of use prescribed
- Concomitant treatment(s) ongoing or written at the time of prescription
- Main reasons for choosing systemic thiocolchicoside
- Information and recommendations provided to the patient when prescribing systemic thiocolchicoside containing medicinal products.

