**Table 9.7.1–1: Mock table to implement in the statistical and study reports**

Country	Question 1...				
	General practitioners	Rheumatologists	Orthopedists / orthopedic surgeons	All (unweighted)	All (weighted)
France	(N=xx)	(N=xx)	(N=xx)	(N=xx)	(N=xxx)
answer 1	xx (xx.x%)	xx (xx.x%)	xx (xx.x%)	xx (xx.x%)	xx (xx.x%)
answer 2	xx (xx.x%)	xx (xx.x%)	xx (xx.x%)	xx (xx.x%)	xx (xx.x%)
answer 3	xx (xx.x%)	xx (xx.x%)	xx (xx.x%)	xx (xx.x%)	xx (xx.x%)
Greece	(N=xx)	(N=xx)	(N=xx)	(N=xx)	(N=xx)
answer 1	xx (xx.x%)	xx (xx.x%)	xx (xx.x%)	xx (xx.x%)	xx (xx.x%)
answer 2	xx (xx.x%)	xx (xx.x%)	xx (xx.x%)	xx (xx.x%)	xx (xx.x%)
answer 3	xx (xx.x%)	xx (xx.x%)	xx (xx.x%)	xx (xx.x%)	xx (xx.x%)
Italy	(N=xx)	(N=xx)	(N=xx)	(N=xx)	(N=xx)
answer 1	xx (xx.x%)	xx (xx.x%)	xx (xx.x%)	xx (xx.x%)	xx (xx.x%)
answer 2	xx (xx.x%)	xx (xx.x%)	xx (xx.x%)	xx (xx.x%)	xx (xx.x%)
answer 3	xx (xx.x%)	xx (xx.x%)	xx (xx.x%)	xx (xx.x%)	xx (xx.x%)
Portugal	(N=xx)	(N=xx)	(N=xx)	(N=xx)	(N=xx)
answer 1	xx (xx.x%)	xx (xx.x%)	xx (xx.x%)	xx (xx.x%)	xx (xx.x%)
answer 2	xx (xx.x%)	xx (xx.x%)	xx (xx.x%)	xx (xx.x%)	xx (xx.x%)
answer 3	xx (xx.x%)	xx (xx.x%)	xx (xx.x%)	xx (xx.x%)	xx (xx.x%)
Overall - unweighted results	(N=xx)	(N=xx)	(N=xx)	(N=xx)	(N=xxx)
answer 1	xx (xx.x%)	xx (xx.x%)	xx (xx.x%)	xx (xx.x%)	xx (xx.x%)
answer 2	xx (xx.x%)	xx (xx.x%)	xx (xx.x%)	xx (xx.x%)	xx (xx.x%)
answer 3	xx (xx.x%)	xx (xx.x%)	xx (xx.x%)	xx (xx.x%)	xx (xx.x%)
Overall - weighted results	(N=xx)	(N=xx)	(N=xx)	(N=xx)	(N=xxx)
answer 1	xx (xx.x%)	xx (xx.x%)	xx (xx.x%)	xx (xx.x%)	xx (xx.x%)
answer 2	xx (xx.x%)	xx (xx.x%)	xx (xx.x%)	xx (xx.x%)	xx (xx.x%)
answer 3	xx (xx.x%)	xx (xx.x%)	xx (xx.x%)	xx (xx.x%)	xx (xx.x%)

Note: the table structure may be adjusted in the final study report.

All the analysis will be descriptive in nature and no statistical comparison will be done in this study, as it does not appear to be necessary to answer suitably the survey objectives. Besides as the DHPC and EM were already distributed to all physicians of the selected specialties, a before-after study design with comparison to baseline values is not possible, as well as a case-control study.

Continuous variables will be described by their number (of valid cases, of missing values), mean, standard deviation, and median, Q1, Q3, minimum and maximum.

Categorical variables will be described as the total number and relative percentage per category. These will be the percentage per category.

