#### Analysis of the collected prescriptions:

The variables will be analysed separately for GPs, rheumatologists and orthopaedists / orthopaedic surgeons according to the information provided, as detailed above in § 9.3: Variables.

Possible selection bias will be assessed by comparing the distributions of available characteristics (e.g. country, age, gender, type of practice and specialty) between respondent and non-respondent physicians.

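### The 12-month look-back for reported prescriptions starts before the educational materials (EM) went out in France and Greece, and the stated analysis does not separate prescriptions written before and after them

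*Protocol*

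**What the plan says.** Section 8.2 sets the aim: "The survey objective is to measure the effectiveness of the DHPC and EM, implemented as part of RMMs". It is to be met through the proportion of physicians who understood and implemented the prescribing conditions.

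Part of the evidence on implementation comes from prescriptions that physicians recall. Section 9.5.2, on the sample of collected prescriptions, states: "Physicians are requested to report up to 5 last prescriptions of systemic thicolchicoside written over the last 12 months before the survey". The same window applies in all four countries, and the data are to be used for proportions of appropriate use.

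The timing is in sections 4.10 and 6:
- Fieldwork: "Start of data collection: September 2016" and "End of data collection: November 2016".
- EM distribution: Portugal "September 2015", Italy October 2015, France 26 April 2016, Greece 2 August 2016.
- DHPC distribution: April 2014 in France, February 2014 in the other three countries.

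Section 9.3, item 6, lists "Approximate date of prescription of systemic thiocolchicoside" among the data collected. The stated analysis in section 9.7.1 is: "The variables will be analysed separately for GPs, rheumatologists and orthopaedists / orthopaedic surgeons according to the information provided". The same section says that "a before-after study design with comparison to baseline values is not possible".

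**The concern.** A prescription written before the EM reached a country cannot show that the EM were put into practice there. The look-back is uniform, but EM distribution is spread over almost a year. In France and Greece the window opens before the EM whatever the survey date; in Italy and Portugal it hardly does.

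If the EM improve prescribing, mixing pre-EM prescriptions into the result pulls the apparent implementation of the combined measures downward, by an amount that differs between countries. The mock table in section 9.7.1 sets the countries one under another, so a reader may take a difference in time since the EM for a difference in practice. France holds 58.8% of the target physicians (Table 9.5.2–2), so any French dilution could also carry into weighted overall figures.

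**Working it through.** **1. The plan's own count.** Section 9.5.2 expects about 900 prescriptions. 600 physicians × 0.50 contributing × 3 each = 900, so it reproduces.

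**2. Pre-EM share of the calendar window.** Share = days from (survey date − 12 months) to the EM date, divided by 366, since each window contains 29 February 2016.

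| Survey date | Greece | France | Italy | Portugal |
|---|---|---|---|---|
| 1 Sep 2016 | 336/366 = 92% | 238/366 = 65% | 8–16% | 0–8% |
| 15 Oct 2016 | 292/366 = 80% | 194/366 = 53% | 0–4% | 0% |
| 30 Nov 2016 | 246/366 = 67% | 148/366 = 40% | 0% | 0% |

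The ranges for Italy and Portugal arise because only the month of distribution is given. If prescriptions were spread evenly over the window, and the 900 divided by country as the physicians are (270 France, 180 Greece, 270 Italy, 180 Portugal), about 230 to 400 would be pre-EM. That is a ceiling-type figure, for the reason in step 3.

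**3. What the last five would cover.** The protocol states no volume per physician, but Tables 7.1–1 and 9.5.2–2 together imply an average:
- Greece: 400,976 / 5,808 = 69 a year. Five take 5 × 365/69 ≈ 26 days. Time since the EM is 30, 74 and 120 days on the three survey dates.
- France: 3,072,412 / 95,919 = 32 a year. Five take 5 × 365/32 ≈ 57 days. Time since the EM is 128, 172 and 218 days.

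An average prescriber's last five are therefore mostly post-EM. The averages are rough. The numerators cover all prescribers, the denominators include physicians who never prescribe the drug, and the Greek count lacks rheumatologists.

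**4. Pre-EM share of reported prescriptions, by assumed volume.** This is a simulation with prescribing at a constant random rate, keeping the last five or fewer within 12 months. The three figures are for surveys on 1 September, 15 October and 30 November.

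| Assumed volume | Greece | France |
|---|---|---|
| 0.5 per month | 89 / 73 / 56% | 54 / 39 / 26% |
| 1 per month | 80 / 52 / 29% | 26 / 12 / 5% |
| 4 per month | 29 / 1 / 0% | about 0% |
| Everyone at the implied average | 12 / 0 / 0% | about 0% |
| Implied average, strongly skewed between physicians (gamma, shape 1; assumed) | 34 / 15 / 8% | 15 / 9 / 6% |

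**5. Effect on a proportion.** Pooled proportion = (1 − s) × post-EM proportion + s × pre-EM proportion, where s is the pre-EM share. The understatement is s × (post − pre). The EM effect is unknown. If it were 10 percentage points (assumed), the skewed case on 1 September gives 0.34 × 10 = 3.4 points in Greece and 0.15 × 10 = 1.5 points in France. For an assumed effect of 5 to 20 points, the ranges are 1.7–6.8 and about 0.8–3.0.

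**The case against.** Most of the case on the other side stands, and it limits the point without removing it.

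- **The window shares are not shares of prescriptions.** A reader might infer that 67–92% of Greek prescriptions will predate the EM. The documents do not support that: only the last five are requested, and the implied volumes make most of them recent. Fieldwork is six to seven weeks (section 9.6.1), so the two outer survey dates cannot both apply. On the other side, section 9.5.2 expects only three prescriptions per contributor, below the cap of five. If that reflects low volume rather than reporting burden, the cap does little to shorten the window for many contributors.
- **Every reported prescription postdates the DHPC.** The window opens in September 2015 at the earliest, about 16 months after the last DHPC mailing. The DHPC carries every specific objective in section 8.2: indication, chronic use, dose and duration, pregnancy and lactation, contraception. Pre-EM prescriptions are sound evidence on those conditions. No separate EM result is planned, so the weakness concerns only what the prescriptions say about the two measures together.
- **The core questionnaire is untouched.** Knowledge, awareness and intention are measured after the EM in all four countries, and the sample size of 600 rests on them. Section 9.9.4 already asks for caution with the prescription section, although it names recall and selection, not this problem.
- **The date may yet be used.** It is among the section 9.3 variables to which the analysis refers, and an SAP, not shown here, could split on it. The protocol does not say that prescriptions will be treated as post-EM. What it fixes is one uniform window and an analysis by specialty.
- **The before-after statement.** A reader might infer that it is wrong, since the data straddle the EM in two countries. But nothing in the window precedes the DHPC, so the statement holds for a pre-DHPC baseline. A contrast around the EM date would also be confounded: under last-five reporting, older prescriptions come mainly from low-volume prescribers.

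**Conclusion.** The point holds for the prescription section only. In France and Greece the look-back reaches behind EM distribution throughout fieldwork, and the stated analysis does not separate the two periods although a date is collected.

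The size depends on prescribing volume, which the protocol gives only through crude averages. At those averages the pre-EM share of reported prescriptions is near zero in France and at most about 12% in Greece. With strong skew between physicians it is about 6–15% in France and 8–34% in Greece. It becomes large only for physicians writing about one prescription a month or fewer, and for early Greek responders.

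The direction, understating implementation of DHPC plus EM, assumes that the EM have some beneficial effect. The documents do not support reading this as a flaw in the knowledge and attitude results, or as a bias in a formal country comparison, since none is planned. It is worth correcting because it affects how the prescription results are read and the correction needs no new data.

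**What to change.** 1. From the approximate prescription date, derive an indicator of whether each prescription falls before or after EM distribution in its country.
2. In section 9.7.1, report the prescription results by country for post-EM prescriptions (evidence on DHPC plus EM) and separately for earlier ones (DHPC-only period), beside the pooled result.
3. State that any contrast between the two periods is descriptive only, because dates are recalled and prescriber volume confounds it.
4. Keep the before-after statement in section 9.7.1, but narrow it to say that no pre-DHPC baseline exists.
5. Add the issue to the limitations in section 9.9.4.

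The cost is one derived variable, one extra table split and a few sentences. The post-EM tables for Greece and France will hold fewer prescriptions, and approximate dates will put some on the wrong side of the cut-off, most of all in Greece, where the EM went out shortly before fieldwork. Italy and Portugal will have almost no earlier period to show.
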